7.12.6. Vital Signs and Other Physical Findings

The analysis of vital sign parameters is described in Study CPMP SAP Version 5.

Vital signs will be reported separately for the 8-week treatment period and the entire 10-week study period.

7.12.7. Electrocardiograms

The analysis of ECG parameters is described in Study CPMP SAP Version 5. ECGs will be reported separately for the 8-week treatment period and the entire 10-week study period.

7.12.8. Suicidal Ideation or Behavior

Reporting of suicidal ideation/behavior through the Columbia Suicide-Severity Rating Scale has been described in Study CPMP SAP Version 5. Suicidal ideation/behavior will be reported separately for the 8-week treatment period and the entire 10-week study period.

7.13. Subgroup Analyses

General subgroup analyses are described in Study CPMP SAP Version 5. There are no additional subgroup analyses planned.

7.14. Protocol Deviations

Participants with study important protocol deviations will be summarized by type of deviation and listed by treatment and investigative site.

Important protocol deviations for the study are described in Study CPMP and Study NP05 Trial Issue Management Plans.

7.15. Interim Analyses and Data Monitoring

Safety review will be conducted under the auspices of an Assessment Committee according to the specifications set forth in the protocol. These analyses will be at the CPMP level and will consider data from all ongoing ISAs. Details are provided in Study CPMP SAP Version 5. No

interim analyses are planned for Study NP05. Unplanned interim analyses may be conducted for reasons including futility analyses, early efficacy analyses, safety analyses, or other analyses, if deemed needed for key business decisions and planning.

7.16. Planned Exploratory Analyses

The following analyses may be conducted for exploratory purposes:

In addition, a cumulative distribution function of percent change from baseline to endpoint for the following BPI-SF score will be provided for each treatment group:

- mean interference score
- mean severity score
- individual severity scores, and
- individual interference scores.

However, no statistical comparisons will be made between the groups.

7.17. Totality of Evidence for Efficacy

The totality of evidence analysis approach for efficacy data has been briefly described in Study CPMP SAP Version 5. A multivariate Bayesian model will be fit within each ISA to assess efficacy ToE across domains. To inform the aggregation of model-based estimates for domain scores, important weights for each scale within a domain are described in Table NP05.7.3.

7.18. Totality of Evidence for Safety

The totality of evidence analysis approach for safety data has been briefly described in Study CPMP SAP Version 5. The key safety events to be considered for Study NP05 are listed below by domain:

General adverse event information

[figure not shown]
- Serious adverse events including death related to study treatment
- Study discontinuation due to adverse event
- Treatment discontinuation due to adverse event.

Cardiovascular

- QTcF prolongation: >60 msec increase or QTcF >500 msec
- Serious cardiac disorders adverse event.

Liver function

• Drug-induced liver injury: at least 1 of the following 2 conditions:

Metabolic function

- Serious hypoglycemia AE
- Serious hyperglycemia AE
- Treatment-emergent hemoglobin A1c: Shift from low/normal at baseline to high at least once.

Renal function

- Treatment-emergent abnormal eGFR: Shifts
 - Mild at baseline to moderate/severe
 - o Moderate at baseline to severe.

Neurologic function

- Treatment-emergent abnormal shift on the overall neurologic assessment
- Serious neurologic events
- Seizures FMQ both narrow and broad terms.

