1.1. Synopsis

ISA Title:

Randomized, Placebo-Controlled, Phase 2 Clinical Trial to Evaluate LY3857210 for the Treatment of Diabetic Peripheral Neuropathic Pain

Brief Title: Phase 2 Clinical Trial to Evaluate LY3857210 for the Treatment of Diabetic Peripheral Neuropathic Pain

Regulatory Agency Identifier Numbers:

LY3857210 IND: 156411

Master Protocol IND: 144915

Rationale:

The purpose of this study is to test whether LY3857210 is efficacious in decreasing diabetic peripheral neuropathic pain (DPNP). LY3857210 is a small molecule receptor antagonist of the P2X7 receptor, an adenosine triphosphate ligand-gated ion channel known to be involved in neuroinflammation and pain.

Data will be collected to assess the safety and tolerability of LY3857210 in this study population. The pharmacokinetics of LY3857210 will also be explored. The totality of data from this proof-of-concept study will assess the benefits and risks associated with LY3857210 and inform decisions for the clinical development of LY3857210.

Objectives, Endpoints, and Estimands:

The primary and secondary objectives and endpoints are stated in the Master Protocol H0P-MC-CPMP (CPMP) and the DPNP disease-state addendum (DSA; H0P-MC-CPMP[3]).

Overall Design:

This is a 10-week Phase 2, randomized, double-blind, placebo-controlled study that will compare LY3857210 versus placebo in participants with DPNP.

Study Population:

In addition to inclusion and exclusion criteria described in Master Protocol CPMP and DSA CPMP(3), individuals may not take part in the study if they have

• an eGFR of less than 30 mL/min/1.73 m.

Number of Participants:

Up to approximately 125 participants will be randomly assigned to study intervention with the assumption that 20% of the participants will drop out prior to the end of the double-blind treatment period.

Intervention Groups and Duration:

This double-blind study includes an 8-week treatment period with a 2-week follow-up visit off treatment.

Intervention Name	LY3857210	Placebo
Dosage Level(s)	45 mg daily	Not applicable
Route of Administration	PO	PO
and Duration		

Abbreviation: PO = by mouth.

[figure not shown]
Ethical Considerations of Benefit/Risk:

Taking into account the measures taken to minimize risk to participants participating in this study, the potential risks identified in association with LY3857210 are justified by the anticipated benefits that may be afforded to participants with DPNP.

Data Monitoring Committee: Yes

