	7.12.1.	Adverse Events	
	7.12.3.	Deaths, Other Serious Adverse Events, and Other Notable	
	_	Adverse Events	15

Page	3
------	---

	7.12.4.	Neurological Exam	15
	7.12.5.	Clinical Laboratory Evaluation	15
	7.12.6.	Vital Signs and Other Physical Findings	16
	7.12.7.	Electrocardiograms	16
	7.12.8.	Suicidal Ideation or Behavior	16
7	.13. Sub	ogroup Analyses	16
7	.14. Pro	tocol Deviations	16
7	.15. Inte	erim Analyses and Data Monitoring	16
7	.16. Pla	nned Exploratory Analyses	17
7	.17. Tot	ality of Evidence for Efficacy	17
7	.18. Tot	ality of Evidence for Safety	18
7	.19. Anı	nual Report Analyses	18
7	.20. Clii	nical Trial Registry Analyses	19
8.	Unblin	nding Plan	20
9.	Refere	nces	21

3. Abbreviations and Definitions

[figure not shown]
Term	Definition
AE	adverse event
ALT	alanine aminotransferase
API	average pain intensity
AST	aspartate aminotransferase
BPI-SF	Brief Pain Inventory-Short Form
вма	Bayesian model averaging
cLDA	constrained longitudinal data analysis
compliance	Adherence to all study-related, good clinical practice (GCP), and applicable regulatory requirements.
CPMP	H0P-MC-CPMP
CTR	Clinical Trial Registry
ECG	electrocardiogram
eCOA	Electronic Clinical Outcome Assessment
eGFR	estimated glomerular filtration rate
enroll	The act of assigning a participant to a treatment. Participants who are enrolled in the study are those who have been assigned to a treatment.
FDA	United States Food and Drug Administration
FMQ	FDA Medical Query
GFR	glomerular filtration rate
ISA	intervention-specific appendix
LLT	Lowest Level Term
LY	LY3857210
MedDRA	Medical Dictionary for Regulatory Activities
MMRM	mixed-effect model for repeated measures
NP05	H0P-MC-NP05
NRS	numeric rating scale

Term	Definition
participant	Equivalent to CDISC term "subject": an individual who participates in a clinical trial, either as recipient of an investigational medicinal product or as a control
PDEP	preliminary data entry period
PK/PD	pharmacokinetics/pharmacodynamics
CCI	
РТ	Preferred Term
PTEAE	posttreatment-emergent adverse event
QTcF	Fridericia's corrected QT interval
SAP	statistical analysis plan
SMQ	standardized MedDRA query
TEAE	Treatment-emergent adverse event: An untoward medical occurrence that emerges during a defined treatment period, having been absent pretreatment, or worsens relative to the pretreatment state, and does not necessarily have to have a causal relationship with this treatment.
ТоЕ	totality of evidence
ULN	upper limit of normal
VAS	visual analog scale

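### One item in the safety totality of evidence is filtered by a causality judgement, and the SAP does not make clear whether the filter covers all serious adverse events or only deaths

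*SAP*

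**What the plan says.** SAP 7.18 introduces its list with "The key safety events to be considered for Study NP05 are listed below by domain". Under general adverse event information, the first visible entry is "Serious adverse events including death related to study treatment". Discontinuation from the study and from treatment follow, the former worded "Study discontinuation due to adverse event". The organ-system domains include "Serious cardiac disorders adverse event", serious hypoglycemia and hyperglycemia, "Serious neurologic events" and a seizure query. None of these other entries mentions relatedness.

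The method is set out elsewhere: "The totality of evidence analysis approach for safety data has been briefly described in Study CPMP SAP Version 5". That master-protocol SAP is not among the supplied documents.

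Two further statements bear on the point. The SAP's definition of a treatment-emergent adverse event (section 3) says that such an event "does not necessarily have to have a causal relationship with this treatment". The protocol synopsis describes the design: "This is a 10-week Phase 2, randomized, double-blind, placebo-controlled study that will compare LY3857210 versus placebo in participants with DPNP".

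**The concern.** In a blinded randomized comparison, the control arm supplies the background rate, so an excess of serious events on active drug can be seen without anyone deciding case by case what caused each event. A relatedness filter puts an individual judgement ahead of that comparison. The judgement is least reliable for an effect that nobody yet expects. For example, protocol 2.3.1 says that no clinical drug-drug interaction studies have been done and that in vitro data point to possible enzyme induction. A serious event arising through a concomitant drug could plausibly be judged unrelated.

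At stake is whether the ToE gives a complete account of the gravest outcomes. With up to about 125 participants, SAEs may be few, so each event left out could matter. The unclear wording is a fault in itself: two programmers could build different variables from the same line. No supplied text gives a reason for the filter or says who makes the judgement for this item.

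**Working it through.** The SAP attaches no figure to this item, so there is none to reproduce. The main check compares texts.

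**Step 1: is the filter particular to this item?** In SAP 7.18, the two discontinuation items, the serious cardiac, glycemic and neurologic items and the seizure query carry no relatedness condition. The QTcF, liver, hemoglobin A1c, eGFR and neurologic-assessment items are defined by measurements or findings as far as they can be read. The treatment-emergent definition in section 3 does not require causality either. The item stands alone among those visible.

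**Step 2: what drops out under each reading?**

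- *Broad reading (the filter applies to all SAEs).* An unrelated SAE still enters the ToE if it is a serious cardiac, hypoglycemic, hyperglycemic or neurologic event, a seizure term, or a cause of discontinuation. Otherwise it enters no visible item. A serious infection judged unrelated, with dosing continued, is an example.
- *Narrow reading (the filter applies to deaths only).* All non-fatal SAEs count, and deaths judged unrelated are left out of this item. Some may enter through an organ-system item. Whether a death is also coded as a discontinuation due to an adverse event cannot be told, because SAP 7.6 refers disposition to the master-protocol SAP.

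A death is itself an SAE, so the broad reading is the more natural one, but the wording does not settle it.

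**Step 3: are the events lost elsewhere?** SAP 7.20 summarizes serious events by treatment group and preferred term, with participants at risk, participants affected and event counts. SAP 7.19 provides a cumulative SAE summary and a listing of deaths. Neither states a causality filter.

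**Step 4: illustration only, broad reading.** All rates here are assumed. Take 62 per arm (about 125/2, with 1:1 allocation assumed) and true SAE rates of 8% on LY3857210 and 2% on placebo. Let X and Y be the numbers affected on LY3857210 and placebo, independent binomials with n = 62. The expected count is 62 × rate × share judged related. The last column is the chance that X − Y is at least 2.

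| Events counted | Expected X vs Y | P(X − Y ≥ 2) |
|---|---|---|
| All SAEs | 62 × 0.08 = 5.0 vs 62 × 0.02 = 1.2 | 82% |
| 50% judged related in both arms | 2.5 vs 0.6 | 56% |
| 25% judged related in both arms | 1.2 vs 0.3 | 29% |
| 10% judged related in both arms | 0.5 vs 0.1 | 8% |
| Only the 6-point excess judged related | 62 × 0.06 = 3.7 vs 0 | 89% |

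If both arms have a true rate of 2%, counting all SAEs gives an LY3857210 excess of at least 2 in 16% of trials.

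The direction therefore depends on how good the judgement is. A filter that keeps the same share in both arms hides an imbalance, while one that picks out exactly the drug-caused events sharpens it. The documents do not say which is closer to the truth. None of these figures applies under the narrow reading.

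**The case against.** The strongest reply is that little is lost. Serious events in the domains that the sponsor singled out enter the ToE whatever their cause, as do events that lead to discontinuation, and unfiltered SAE summaries appear elsewhere in the SAP. Counting related SAEs in a compact summary is a recognizable choice in a phase 2 proof-of-concept study. If investigators judge well, the filter removes background noise, as the 89% and 16% figures in the illustration show. The ToE method, and perhaps a master list that includes all SAEs, sits in a document that was not supplied. A figure is also missing just above the item, so an unseen companion entry cannot be excluded.

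Most of this stands as a limit on scope. It does not remove the point. The list for this study is defined in SAP 7.18, so its wording has to be settled there. Registry and annual-report outputs do not put an event into the ToE. The possible gain from accurate judgement remains available if the related subset is shown beside the full count.

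A reader might infer more: that unrelated SAEs and deaths vanish from the placebo comparison, or that the filter would erase a real imbalance. The documents do not support either. SAP 7.20 keeps serious events by arm with no stated filter, several ToE items catch unrelated events, and the effect on an imbalance turns on unknown relatedness shares. That the ToE itself contrasts the arms is inferred from the design; SAP 7.18 does not say so.

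**Conclusion.** The point holds within these limits. The SAE and death item is the only visible key safety event in SAP 7.18 that is subject to a causality judgement, its reach is ambiguous, and under either reading some serious events are left out of it without a stated reason. The consequence is confined to the safety ToE. Its size cannot be estimated, because the documents give no SAE rates, relatedness shares or allocation ratio. The percentages in the illustration rest on assumed rates and on opposite assumptions about relatedness, and should not be quoted as the size of the effect. The conclusion also assumes that neither the master-protocol SAP nor the missing figure supplies an all-causality SAE item for this ToE.

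**What to change.** Reword the item in SAP 7.18 as: *Serious adverse events, including death, regardless of relationship to study treatment*. Summarize it by arm, and show the subset judged related as a supporting row. This settles the ambiguity and brings the item into line with the rest of the list.

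If the sponsor prefers to keep the filter, the SAP should say whether it applies to all SAEs or only to deaths, why it is used, and who judges relatedness under blind.

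The cost is a few words in the SAP and one extra row in the output, with no change to data collection. The small downside is more background SAEs in both arms of the main row; the supporting row keeps the filtered view available.

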7.12.4. Neurological Exam

In this ISA, neurological exam results will be reported for the entire 10-week study period. Study NP05 will consider the following analyses for the Neurological Exam, which evaluates 6 items and will be summarized by normal/abnormal percentage by item. In addition, we will summarize shift tables for each item in the Neurological Exam.

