7.12.5. Clinical Laboratory Evaluation

The general analysis of laboratory parameters is described in Study CPMP SAP Version 5.

In this ISA, laboratory results will be reported for the entire 10-week study period. Study NP05 will also consider the following analyses of lab analytes used to assess renal function. The planned summaries for these analytes are the same as those that have been described in Study CPMP SAP Version 5. However, the reporting of these analytes will be separate from the general analysis of laboratory parameters.

- Renal data analyses:
 - o serum creatinine (change from baseline in mg/dL)
 - o eGFR; Chronic Kidney Disease Epidemiology Collaboration (algorithm using serum creatinine) Algorithm: Provided by central laboratory

- for eGFR calculation, we will summarize shift tables of eGFR changes for baseline versus postbaseline by minimum, maximum, and last observed eGFR result:
 - Category 1: Normal or increase in GFR (≥90 mL/min/1.73 m²)
 - Category 2: Mild reduction in GFR (60 to 89 mL/min/1.73 m²)
 - Category 3a: Moderate (a) reduction in GFR (45 to 59 mL/min/1.73 m²)
 - Category 3b: Moderate (b) reduction in GFR (30 to 44 mL/min/1.73 m²)
 - Category 4: Severe reduction in GFR (15 to 29 mL/min/1.73 m²)
 - Category 5: Kidney failure (GFR <15 mL/min/1.73 m² or dialysis).

Abnormal eGFR is specified below and will be summarized in the laboratory summary tables.

- Abnormal low: <90 mL/min/1.73m²
- Abnormal high: As specified by central laboratory.

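### The only HbA1c event visible in the SAP 7.18 key safety list cannot be recorded for a participant whose HbA1c is already high at baseline, in a trial where every participant has diabetes

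*SAP*

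**What the plan says.** SAP 7.18 names the key safety events by domain. Its metabolic domain has three visible entries: serious hypoglycaemia, serious hyperglycaemia, and "Treatment-emergent hemoglobin A1c: Shift from low/normal at baseline to high at least once". The third is the only one based on HbA1c.

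Other entries in the same list treat baseline differently:

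- The cardiovascular domain has "QTcF prolongation: >60 msec increase or QTcF >500 msec", whose first part is a change that can occur from any starting value.
- The renal domain counts worsening from reduced categories, for example "Mild at baseline to moderate/severe".
- The neurologic domain has "Treatment-emergent abnormal shift on the overall neurologic assessment".
- The general block includes "Study discontinuation due to adverse event" and the matching item for treatment discontinuation.

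The Protocol synopsis describes a study that will "compare LY3857210 versus placebo in participants with DPNP", so all participants have diabetes. The NP05 schedule (Protocol 1.3) takes HbA1c at V3, V7 and early discontinuation (ED). SAP 7.12.5 adds NP05-specific renal analyses but none for HbA1c. For the rest it says: "The general analysis of laboratory parameters is described in Study CPMP SAP Version 5". That document was not supplied.

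**The concern.** A low/normal-to-high shift is a usual way to count new laboratory abnormality, and it works well when most participants start in range. Here the disease under study brings with it a condition that can put the marker above range before dosing. Participants who start high are outside the reach of the event, so the metabolic domain has no HbA1c-based way to register worsening in them.

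What is at stake is how the domain is read. A low count could mean little worsening, or it could mean that few participants were able to have the event. Without the number at risk, a reader cannot separate the two.

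**Working it through.** The plan states no figure on this point, so there is none to reproduce. The check is to apply the rule to every case and then see how the number at risk depends on the unknown baseline share.

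**Step 1: apply the rule.** Cross baseline category with the highest postbaseline category.

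| Baseline | Postbaseline low | Postbaseline normal | Postbaseline high |
|---|---|---|---|
| Low | no event | no event | event |
| Normal | no event | no event | event |
| High | no event | no event | no event |

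Two of nine cells are events. All three cells with a high baseline are non-events, whatever the size of the rise.

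**Step 2: other routes into the list.** Among the visible items, a rise from a high baseline can enter 7.18 through a serious adverse event (general or hyperglycaemia) or through an AE-related study or treatment discontinuation. A figure is missing from the general adverse event block in the text available for review, so this statement covers the visible items only.

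**Step 3: number at risk.** Inputs:

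- N = 125, the approximate maximum randomized, and 20% dropout (Protocol 1.1).
- p, the share high at baseline. It is not in the documents, so it is assumed and varied.

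Upper bound on the number at risk, both arms together = 125 × (1 − p). It is an upper bound because it gives every participant a postbaseline value. If instead none of the 20% who drop out has one, and dropout is unrelated to baseline HbA1c, the number is 125 × 0.80 × (1 − p) = 100 × (1 − p).

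| Assumed p | 125 × (1 − p) | 100 × (1 − p) |
|---|---|---|
| 0.25 | 93.75 | 75 |
| 0.50 | 62.5 | 50 |
| 0.70 | 37.5 | 30 |
| 0.90 | 12.5 | 10 |
| 0.95 | 6.25 | 5 |

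**Step 4: per arm.** Protocol 6.3 leaves randomization to the Master Protocol, so the allocation ratio is a second assumption. As upper bounds:

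- 1:1, p = 0.50: 62.5 / 2 = 31.25 per arm. At p = 0.95: 6.25 / 2 = 3.1.
- 2:1, p = 0.50: 62.5 × 2/3 = 41.7 on LY3857210 and 62.5 / 3 = 20.8 on placebo. At p = 0.95: 4.2 and 2.1.

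The range is wide because the documents do not fix p. It shows how the count depends on p; it does not estimate the count.

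**Step 5: compare with the rest of the list.** The list is mixed. The QTcF increase and the eGFR shifts from mild or moderate can register worsening from an abnormal baseline. On the other hand, the eGFR rule lists no shift from normal. The neurologic item may share the HbA1c limit: SAP 7.12.4 has the exam "summarized by normal/abnormal percentage by item", but 7.18 refers to an overall assessment that the supplied text does not define. The comparison shows that an any-baseline event already has a place in this list. It does not show that HbA1c is the only item with a restricted starting state.

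**The case against.** The strongest reply is that the shift does what its label says: it counts new abnormality. It has no stated role in any decision, and no glycaemic signal for the drug is described. Non-serious worsening reported as an adverse event would still be tabulated by preferred term (SAP 7.12.3), though outside this list. CPMP SAP Version 5 governs both the general laboratory analysis and the totality-of-evidence approach. It may already set denominators or summarise HbA1c change, so parts of the remedy may exist. The one addition that does not depend on Version 5 needs an increment for which the documents offer no value.

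Most of this stands and limits the weight of the point. It does not remove it, because Version 5 cannot alter which participants this event, as written for NP05, is able to count.

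A reader might also infer from an all-diabetic population that most participants start high and that the event is close to impossible. The documents do not support that. Diabetes alone does not place HbA1c above a given limit, the limit for high is not stated, and most eligibility criteria sit in the Master Protocol and disease-state addendum (Protocol 5). Nor can it be inferred that HbA1c worsening goes unreported in the trial as a whole.

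**Conclusion.** The point holds as a limit of one event definition. In the visible text of SAP 7.18, no participant who is high at baseline can have the HbA1c event. That follows from the definition alone, and confidence in it is high.

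The impact is unknown. It depends on the share high at baseline and on the limit for high, neither of which is given. The counts above are illustrations and upper bounds. How much of the gap remains in reporting depends on CPMP SAP Version 5. The primary result is not affected. This is a cheap improvement to consider, not an error that must be corrected.

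**What to change.** In SAP 7.18:

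1. Keep the existing shift, but report it by arm with the number at risk: participants low or normal at baseline who have a postbaseline value.
2. Add one HbA1c increase-from-baseline event, V3 to V7 or ED, that can occur at any baseline. The sponsor should set the increment before unblinding. If unblinding has already taken place, label the event post hoc.
3. Report baseline-adjusted HbA1c change by arm, if CPMP SAP Version 5 does not already do so.

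The cost is SAP wording and at most a small extra analysis of values already scheduled at V3, V7 and ED. No new visit or sample is needed. The downside is one increment to choose and justify, and one more item in the list.

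### The only renal event in the safety totality of evidence omits participants with normal baseline eGFR, so a fall from normal to moderate or worse is not counted there

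*SAP*

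**What the plan says.** SAP 7.18 lists the key safety events for NP05 by domain. Renal function has one item, "Treatment-emergent abnormal eGFR: Shifts", with two rows: "Mild at baseline to moderate/severe" and "Moderate at baseline to severe". No row starts from a normal baseline.

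SAP 7.12.5 defines the eGFR categories (mL/min/1.73 m²): normal, 90 or above; mild, 60 to 89; moderate, 45 to 59 (3a) and 30 to 44 (3b); severe, 15 to 29; kidney failure, below 15 or dialysis. It sets the abnormal-low limit at 90 for the laboratory summary tables. It also plans eGFR shift tables by minimum, maximum and last post-baseline value.

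Protocol 5.2 excludes eGFR below 30 and sets no upper limit, so the ISA allows participants with normal eGFR to enrol.

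Elsewhere in 7.18, the metabolic domain has "Treatment-emergent hemoglobin A1c: Shift from low/normal at baseline to high at least once". The general domain has "Serious adverse events including death related to study treatment" and "Treatment discontinuation due to adverse event", together with study discontinuation due to an adverse event. On method, 7.18 says: "The totality of evidence analysis approach for safety data has been briefly described in Study CPMP SAP Version 5".

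**The concern.** Normal and mild are separate categories in 7.12.5, so mild cannot be read to include normal. A participant who starts at 90 or above therefore cannot register the renal event, however far eGFR falls. Two participants who reach the same level are also classified the wrong way round: the one with the slightly higher baseline, and so the larger loss, is the one not counted.

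The label fits poorly too. If the 90 limit in 7.12.5 is applied, both listed baselines are already abnormal, so an abnormality that is new on treatment can never register. The HbA1c event in the same list does start from a low or normal baseline. This is an inconsistency of approach, not a contradiction between passages.

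What is at stake is the sensitivity of one flag, in both arms. A laboratory fall from normal to moderate or worse, with no treatment-related serious AE and no discontinuation due to an AE, leaves no mark in the renal domain of 7.18.

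**Working it through.** The plan states no figure on this point to reproduce. The check applies the 7.18 rule to the 7.12.5 categories.

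**Category pairs.** The ISA's exclusion below 30 leaves four baseline categories: 1, 2, 3a and 3b. The worsening pairs number 5 + 4 + 3 + 2 = 14.

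| Baseline | Worsening pairs | Counted, kidney failure separate from severe | Counted, severe read as severe or worse | Counted, proposed rule |
|---|---|---|---|---|
| 1 (normal) | 5 | 0 | 0 | 4 |
| 2 (mild) | 4 | 3 | 4 | 4 |
| 3a | 3 | 1 | 2 | 2 |
| 3b | 2 | 1 | 2 | 2 |
| Total | 14 | 5 | 8 | 12 |

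Of the four pairs from normal to moderate or worse (3a, 3b, 4, 5), none is counted under either reading. The proposed rule leaves out only normal to mild and 3a to 3b.

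**Same end value, adjacent baselines.** There are 59 − 15 + 1 = 45 whole-unit end values from 15 to 59. The current rule counts 45 of 45 from baseline 89 and 0 of 45 from baseline 90. The proposed rule counts 45 of 45 from both.

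- 89 to 45: loss 44, 44/89 = 49.4%, counted.
- 90 to 45: loss 45, 45/90 = 50.0%, not counted.
- 95 to 20: loss 75, 75/95 = 78.9%, not counted.
- 60 to 59: loss 1, counted.

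**Smallest loss that goes uncounted, starting from 90.**

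- To moderate: 90 − 59 = 31 (34.4%).
- To severe: 90 − 29 = 61 (67.8%).
- To kidney failure: 90 − 14 = 76 (84.4%).

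**Possible scale.** The documents give no baseline eGFR distribution and no rate of decline, so both are assumed here. The sample size is about 125 (Protocol 1.1).

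- Normal baseline in 20% to 60%: 125 × 0.20 = 25 to 125 × 0.60 = 75 participants who cannot register the event.
- Fall below 60 in 1% to 3% of these: 25 × 0.01 = 0.25 to 75 × 0.03 = 2.25 missed events, or about 0 to 2 participants over both arms.

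**The case against.** The strongest reply is that no renal data are lost. The 7.12.5 shift tables cover all six categories, and serum creatinine change and the below-90 summary are reported as well. A fall from 95 to 20 would appear there by arm. If it were a treatment-related serious AE, or led to discontinuation, it would also enter the general domain of 7.18. All of that stands, and it limits the impact. It does not supply the laboratory-based renal event, which is what this domain is meant to record.

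The weight of the event is also unknown, because the method is in CPMP SAP Version 5, which was not available and could contain renal rules of its own. That stands as a limit on how much the point matters.

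The HbA1c parallel and the below-90 limit, taken strictly, would argue for counting normal to mild as well, which the proposed rule does not do. Any category rule also has edges: after the fix, 60 to 59 is still an event and 120 to 60 (a 50% loss) is still not. Both remarks are fair. The case for change therefore rests mainly on the same-end-value comparison: once 7.18 treats arrival at moderate as an event, a higher baseline should not cancel it.

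Finally, the two liver conditions in 7.18 are missing from the text as read, so a lost renal line cannot be ruled out. Nothing in the renal list suggests one.

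**Conclusion.** The concern holds. As written, the renal event in 7.18 cannot be registered by anyone with normal baseline eGFR, and it classifies 90 to 45 as less notable than 89 to 45. This is a stated rule that misclassifies, not a missing detail.

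The impact is modest: lower sensitivity of one safety flag in both arms, with about 0 to 2 participants affected if 20% to 60% have normal baseline and 1% to 3% of those fall below 60. Those percentages are assumptions. The conclusion on the rule itself does not depend on them. It does assume that the renal list is complete as read and that CPMP SAP Version 5 adds no further renal shift.

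One related point needs only clarification: 7.18 says severe where 7.12.5 separates severe from kidney failure. It may be meant as severe or worse.

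**What to change.** In SAP 7.18, define treatment-emergent abnormal eGFR as either of:

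- normal or mild at baseline to moderate (3a or 3b) or worse;
- moderate at baseline to severe or worse.

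State that or worse includes Category 5. Unless CPMP SAP Version 5 already specifies the post-baseline value, use the minimum, which 7.12.5 already plans. Normal to mild stays uncounted, because 7.18 starts counting at moderate; the 7.12.5 tables show those shifts. If normal baseline was left out on purpose, keep the rule and give the reason in 7.18.

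The cost is two lines of text and one programming change. No new data are needed: the ISA schedule (Protocol 1.3) already has chemistry at V4, V5, V6, V7 and V801. The one downside is a slightly higher renal event count, by 0 to 2 participants under the assumptions above.
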